7. ANALYSIS INTERPRETATION

All analyses are descriptive. The use of these descriptive analyses will be limited to supportive analysis or hypothesis generation.

CONFIDENTIAL201112 (EPI-NTHI-001 BOD APA)
Statistical Analysis Plan Amendment 2 Final**8. CONDUCT OF ANALYSES****8.1. Sequence of analyses**

The analyses will be performed in two steps:

- An interim analysis will be performed when at least 40 AECOPD evaluable sputum samples are available. It will include all data available at the time of analysis. The rate of positive samples will be computed for bacterial pathogen (including Hi, NTHi and Mcat) together and per pathogen. The incidence rate of AECOPD overall and associated to bacterial pathogen will be computed as well. The analysis will be done based on as clean as possible data. No study report will be written at this stage.
- A final analysis of all objectives will be performed when data obtained up to planned last patient last visit are available. A final study report will be written at this stage.

Description	Analysis ID	Disclosure Purpose (CTRS=public posting, SR=study report, internal)	Dry run review needed (Y/N)	Study Headline Summary (SHS)requiring expedited communication to upper management (Yes/No)	Reference for TFL
Final analysis	E1_01	Study report	YES	NO	See TFL TOC
Interim analysis	E1_02	Internal	NO	NO	See TFL TOC

8.2. Statistical considerations for interim analyses

All analyses are descriptive and therefore no statistical adjustment for the interim analysis is required. No study report will be written for interim analysis.

9. CHANGES FROM PLANNED ANALYSES

Not applicable

11.2. Data derivation**11.2.1. COPD severity stage**

The baseline COPD severity stage will be derived by the investigator from the spirometry results at the screening visit. The spirometric classification of airflow limitation in COPD patients is based on post-bronchodilator FEV₁ and can be divided into four GOLD grades (GOLD 1 - mild, GOLD 2 - moderate, GOLD 3 - severe and GOLD 4 - very severe) [Global Initiative for Chronic Obstructive Lung Disease (GOLD). Global strategy for the diagnosis, management, and prevention of Chronic Obstructive Pulmonary Disease, updated 2013. Available from:

http://www.goldcopd.org/uploads/users/files/GOLD_Report_2013_Feb20.pdf]. For the purpose of this study only patients with COPD graded from moderate to very severe will be enrolled.

Table 1 COPD severity stages included in the study

GOLD grade	In patients with FEV₁/FVC<0.70
GOLD 2: Moderate	50% ≤ FEV ₁ < 80% predicted
GOLD 3: Severe	30% ≤ FEV ₁ < 50% predicted
GOLD 4: Very severe	FEV ₁ < 30% predicted

CONFIDENTIAL

201112 (EPI-NTHI-001 BOD APA)
 Statistical Analysis Plan Amendment 2 Final

The resulting COPD severity variable will be used in all models in which COPD at baseline will be taken into account.

A four-grade refined assessment of COPD severity stages will be computed according to the newest GOLD criteria [GOLD, 2017 Global Initiative for Chronic Obstructive Lung Disease (GOLD). Global strategy for the diagnosis, management, and prevention of Chronic Obstructive Pulmonary Disease, updated 2017. Available from: <http://goldcopd.org/gold-2017-global-strategy-diagnosis-management-prevention-copd/>]. In the assessment scheme, patients should undergo spirometry to determine the severity of airflow limitation (i.e., spirometric grade). They should then undergo assessment of either dyspnea using mMRC or symptoms using CAT. Finally, their history of exacerbations (including prior hospitalizations) should be recorded.

For the purpose of this study we will only adopt CAT rather than adopting mMRC dyspnea scale. This choice is because the two tools are not interchangeable [Kim S, Oh J, Kim YI, Ban HJ, Kwon YS, Oh IJ, Kim KS, Kim YC, Lim SC. Differences in classification of COPD group using COPD assessment test (CAT) or modified Medical Research Council (mMRC) dyspnea scores: a cross-sectional analyses. *BMC Pulm Med.* 2013;13:35] and it is now recognized that COPD impacts patients beyond just dyspnea [Jones PW. Health status measurement in chronic obstructive pulmonary disease. *Thorax.* 2001; 56(11):880-7].

The four grades are:

- Patient Group A – Low Risk, Less Symptoms Typically GOLD 1 or GOLD 2 (Mild or Moderate airflow limitation); and 0-1 exacerbation per year and no hospitalization for exacerbation; and CAT score < 10;
- Patient Group B – Low Risk, More Symptoms Typically GOLD 1 or GOLD 2 (Mild or Moderate airflow limitation); and 0-1 exacerbation per year and no hospitalization for exacerbation; and CAT score ≥ 10 ;
- Patient Group C – High Risk, Less Symptoms Typically GOLD 3 or GOLD 4 (Severe or Very Severe airflow limitation); and ≥ 2 exacerbations per year or ≥ 1 with hospitalization for exacerbation; and CAT score < 10;
- Patient Group D – High Risk, More Symptoms Typically GOLD 3 or GOLD 4 (Severe or Very Severe airflow limitation); and ≥ 2 exacerbations per year or ≥ 1 with hospitalization for exacerbation; and CAT score ≥ 10 .

Spirometry results for GOLD classifications, number of exacerbations per year, and number of exacerbation requiring hospitalization will be taken from the screening visit (visit 0). CAT score will be derived from visit 1.

CONFIDENTIAL

201112 (EPI-NTHI-001 BOD APA)
 Statistical Analysis Plan Amendment 2 Final

11.2.2. HRQOL**11.2.2.1. CAT**

The CAT index will be derived as the sum of the ratings recorded for each of the eight individual items. Each of these items has 6 possible scores (0, 1, 2, 3, 4 or 5), leading to a range of 0 to 40 for CAT score.

No missing items are expected because the e-diary system prompts the patient to compete an item of CAT to proceed to the following one. Partial questionnaires will be excluded.

11.2.2.2. SGRQ-C

The SGRQ-C total score will be derived as the weighted sum of the forty individual items leading to a range of 0 to 100 as detailed in the reference manual [St George's Respiratory Questionnaire for COPD patients (SGRQ-C), version 1.3, 2016].

The SGRQ-C symptoms, activity and impacts component scores will be derived as the weighted sum of subset of items as detailed in the reference manual.

No missing missing items are expected because the e-diary system prompts the patient to compete an item of SGRQ-C to proceed to the following one. Partial questionnaires will be excluded.

11.2.3. Sputum Quality

The quality of sputum is defined as follow:

- < 10 squamous epithelial cells/field: sample of good quality
- 10-25 squamous epithelial cells/field with significant numbers of cells derived from the lower respiratory tractus (ciliary epithelial cells, bronchial cells, round cells): sample of moderate quality
- > 25 squamous epithelial cells/field: sample of bad quality

11.2.4. Bacterial and viral PCR assays

- Multiplex real-time PCR (MPB1) assay will target *Haemophilus influenzae*, *Moraxella catarrhalis*, *Streptococcus pneumoniae* with quantitative results (copies/mL of sample).

For qualitative analyses, quantitative results must be converted in POS/NEG results. Only samples above the cut off will be considered as POSITIVE.

The positivity cut-off for each quantitative PCR assay will be defined at time of data release.

For quantitative analyses, only samples with load above the cut off will contribute to mean and SD computation.

CONFIDENTIAL

201112 (EPI-NTHI-001 BOD APA)
 Statistical Analysis Plan Amendment 2 Final

- Multiplex real-time PCR (MPB2) assay will target *Streptococcus pyogenes*, *Staphylococcus aureus*, *Pseudomonas aeruginosa* with qualitative results only (POS/NEG).
- Multiplex reverse transcription PCR assay will target different viral pathogens with qualitative results only (POS/NEG).
- HRV qPCR assay will target HRV with quantitative results (copies/mL).

For qualitative analyses, qualitative and quantitative results will be combined with the following algorithm:

Sample	Allplex HRV result	Allplex HEV result	HRV RT-qPCR	Final HRV result (variable to be derived)
1	POS	NEG	\geq LOD*	POS
2	POS	NEG	< LOD	POS
3	NEG	POS	\geq LOD	POS
4	NEG	POS	< LOD	NEG
5	NEG	NEG	Not tested	NEG
6	POS	NEG	0	POS
7	POS	POS	\geq LOD	POS

*The positivity cut-off for each quantitative PCR assay will be defined at time of data release. For quantitative analyses, only positive samples will contribute to mean and SD computation.

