6.4.3. Load of bacteria and virus

Total number of patients providing a sputum sample, the number of sputum samples positive to specific bacteria (by culture) and the frequencies of semi-quantitative bacteriological load (few scattered, +, ++, +++) will be tabulated at each scheduled [stable] visit and at each exacerbation visit.

Total number of patients providing a sputum sample, the number of sputum sample positive to specific bacteria (by PCR)/HRV and average load will be tabulated at each scheduled [stable] visit and at each exacerbation visit.

CONFIDENTIAL

201112 (EPI-NTHI-001 BOD APA)
 Statistical Analysis Plan Amendment 2 Final

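### PCR bacterial and HRV load is to be summarised by mean and SD of copies/mL among positives, with no log scale, median or quartiles; if loads spread over about 1 log10 or more, the stable-versus-AECOPD comparison is imprecise and can mislead

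*SAP*

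**What the plan says.** SAP 11.2.4 gives quantitative PCR results in copies/mL for *H. influenzae*, *M. catarrhalis*, *S. pneumoniae* and HRV. For the bacteria, "only samples with load above the cut off will contribute to mean and SD computation". For HRV, under the table that derives the final HRV result, the rule reads "For quantitative analyses, only positive samples will contribute to mean and SD computation". No cut-off value is given: "The positivity cut-off for each quantitative PCR assay will be defined at time of data release".

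SAP 6.4.3 describes the output. It counts the patients with a sample and the positive samples, and the load entry beside those counts reads "and average load will be tabulated at each scheduled [stable] visit and at each exacerbation visit". Culture load is handled separately and on an ordinal scale: "the frequencies of semi-quantitative bacteriological load (few scattered, +, ++, +++) will be tabulated".

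Protocol 9.7 promises descriptive summaries of load without naming a statistic. Evaluating load in stable COPD and during AECOPD is a tertiary objective (Protocol 2.3, SAP 3.3), with bacterial and HRV load as tertiary endpoints (SAP 4.3). SAP 7 states that all analyses are descriptive.

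**The concern.** If PCR loads vary over orders of magnitude, the mean and SD of raw copies/mL summarise them poorly. The mean then follows the few largest samples, and the SD says little about the rest.

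The SAP guards against skewed data elsewhere. It plans medians and quartiles for exacerbation length (6.3.5), CAT and SGRQ-C (6.3.6), EXACT scores (6.4.1) and biomarkers (6.4.6), and 6.4.6 switches to a rank correlation if normality fails. PCR load has no such provision.

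No test of load is planned, so a reader who asks whether load is higher during AECOPD has only the tabulated averages and SDs for PCR load. If those averages are unstable, the table can suggest a difference that is not there, or hide or reverse one that is.

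**Working it through.** **1. How many positives enter a mean.** Protocol 9.2 assumes 90% participation, one AECOPD visit each and 80% with an evaluable sample. For 200 enrolled this gives 200 × 0.90 × 1 × 0.80 = 144, against about 140 stated. Table 12 of the protocol considers positivity of 5% to 50% for a specific bacterium. Of 140 samples, 10%, 20% and 30% are 14, 28 and 42 positives. About 30 positives per state is therefore a reasonable working figure for all AECOPD visits together. SAP 6.4.3 tabulates by visit, which divides them further.

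**2. Assumptions.** The documents give no mean, SD, range or distribution of load. I assume lognormal loads with a log10 SD of 0.5, 1.0 or 1.5, independent samples, and equal numbers of positives in the two states.

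**3. No true difference, 30 positives per state.** For geometric means the 95% range of the ratio has a closed form, 10^(±1.96 × SD × √(2/30)). At SD 1.0 the exponent is 1.96 × 0.258 = 0.506, giving 0.31 to 3.2. The arithmetic-mean ranges come from simulation (20,000 replicates).

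| log10 SD | Arithmetic means | Geometric means |
|---|---|---|
| 0.5 | 0.46-2.2 | 0.56-1.8 |
| 1.0 | 0.10-10 | 0.31-3.2 |
| 1.5 | 0.02-59 | 0.18-5.8 |

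At SD 1.0, a spurious difference of threefold or more appears in 32% of replicates on the raw scale and 6% on the log scale.

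**4. True AECOPD/stable ratio of 10^0.5 = 3.16, 28 positives per state.** Percentage of replicates in which the observed ratio points the wrong way, and the median share of total load supplied by the highest samples:

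| log10 SD | Wrong way, arithmetic | Wrong way, geometric | Highest sample | Highest three |
|---|---|---|---|---|
| 0.5 | 0.4% | 0.0% | 19% | 41% |
| 1.0 | 15.6% | 3.1% | 41% | 72% |
| 1.5 | 27.9% | 10.6% | 58% | 89% |

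The observed SD is typically 1.2, 2.4 and 3.3 times the mean in the three cases.

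**5. Which HRV values enter the mean.** In the derivation table of SAP 11.2.4, rows 2 and 6 give a final HRV result of POS with an RT-qPCR result below the LOD (row 2) or of 0 (row 6). Both are positive samples, so the HRV rule as worded admits them to the mean. The bacterial rule requires a load above the cut-off. The two rules therefore differ, and a log10 summary cannot be computed for row 6 because log10 of 0 is undefined.

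**The case against.** The word arithmetic appears nowhere. SAP 11.2.4 is a derivation rule about which samples count, and table layouts are deferred to a separate mock TFL document that is not available here; a log scale or median could be specified there. This stands in part. The raw scale is the literal reading of a mean and SD of results in copies/mL, not an explicit instruction. If log10 was intended, the SAP should still say so.

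The size of the effect rests on an assumed spread. This stands in full. At a log10 SD of 0.5 the choice of scale matters little.

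The simulation compares independent groups, whereas stable and AECOPD samples come from the same patients, and the SAP plans no ratio of loads. Both are fair. The ratio is a way to express how unstable the two tabulated averages are, and its exact range should not be over-read.

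A reader might infer that stable and AECOPD loads cannot be compared at all. The documents do not support that: the number positive stands beside the average, culture load is tabulated in ordinal categories, and SAP 6.3.1 gives the proportion positive by bacterial PCR with confidence intervals. These do not repair the PCR load summary, but they leave other evidence to read.

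A reader might also quote the lognormal coefficient of variation, √(exp((SD × ln 10)²) − 1), which is 14 at SD 1.0 and 389 at SD 1.5. Those are population values. In a table of 30 non-negative values the SD cannot exceed √30 = 5.5 times the mean.

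**Conclusion.** The point holds as a conditional one. As written, the SAP summarises PCR bacterial and HRV load by mean and SD of copies/mL among positives, and gives no log scale, geometric mean, median or quartiles.

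If the spread is about 1 log10 or more, which is an assumption, a few high samples drive the mean. With 30 positives per state and no true difference, the ratio of means then ranges roughly three times further in each direction on the raw scale than on the log scale (10 against 3.2 at the upper end). At a spread of 0.5 log10 the loss is modest.

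The consequence is limited to a tertiary, descriptive objective. No primary or secondary result depends on it. The HRV inclusion rule is a separate small gap that does not depend on the assumed spread.

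**What to change.** Amend SAP 11.2.4 and 6.4.3 to say:

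- PCR bacterial load and HRV load are summarised on the log10 copies/mL scale: geometric mean with 95% CI, SD of log10 load, and median with quartiles.
- The summary uses samples with a quantifiable value at or above the assay cut-off, with the same rule for bacteria and HRV. The number and proportion positive are shown beside it.
- HRV samples with a final result of POS but an RT-qPCR result below the LOD or of 0 (rows 2 and 6) count as positive, do not enter the load summary, and are reported as a number.

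This needs a few sentences in the SAP, a little more table work and no new data. The trade-off is that a geometric mean describes the typical load among quantifiable samples, not the total load; if total load is of interest, the arithmetic mean can be kept as an additional column.

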11.3. Handling missing data

Missing or non-evaluable measurements will not be replaced. The only exception is detailed below.

The number of exacerbations per year will be extrapolated for patients withdrawing from the study to provide an estimate of the number of exacerbations over the one year observation period. The number of exacerbations in a year will be calculated by multiplying the number of exacerbations experienced by the patient by 13 and dividing by the number of 4-week periods the patient was followed up [Stockley R.A., Chopra N, Rice L. Addition of salmeterol to existing treatment in patients with COPD: a 12 month study. *Thorax*. 2006;61:122-128].

$$\text{Number of exacerbations per year} = \frac{\text{Number of exacerbations} * 13}{\text{Number of 4-week observation period intervals}}$$

CONFIDENTIAL

201112 (EPI-NTHI-001 BOD APA)
 Statistical Analysis Plan Amendment 2 Final

The calculation of exacerbation rate will be based on follow-up period intervals of four weeks to avoid obtaining high imputed rates if a patient withdrew very early from the study after experiencing an exacerbation. Four-week intervals will be adopted since treatment courses for moderate/severe exacerbations are <=2 - 4 weeks when appropriate.

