4.1. Number of subjects/ centres

The target is to enrol approximately 200 eligible moderate to very severe COPD patients. Refer to Section 9.2 for a detailed description of the criteria used to estimate the sample size.

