6.3.4. Incidence rates of AECOPD

This study will provide an estimate of average number of exacerbations per person per year, in a COPD population at increased risk of exacerbation (i.e. moderate to very severe COPD patients with a documented history of at least 1 moderate or severe AECOPD in the year prior to enrolment).

To compute the incidence rate all the exacerbations will be taken into account. The observation period is from visit 1 to visit 3 or from visit1 to the last visit performed for patients lost to follow up.

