6.3.4.4. Statistical methods: analysis of count data with overdispersion

The incidence rate and its 95% CI will be estimated using the Generalised Linear Model (GLM) assuming a negative binomial distribution for the response variable with logarithm as link function and the logarithm of follow up time as an offset variable. The fit of the model will be examined using Q-Q plots of standardised residuals. It is possible that the negative binomial model will not converge due to underdispersion of data; in such cases, to overcome the problem of underdispersion, a Poisson model will be used to obtain the incidence rate and its 95% CI.

SAS codes:

```
proc genmod data = <dataset>;
  class gold age smoking exacHist;
  model n_exac = GOLD age smoking exacHist country
    / link=log dist=negbin offset=logfuinyears ;
  ods output parameterestimates=out_parm nobs=nobs;
  ods exclude modelinfo modelfit parameterestimates nobs;
  run;

  data parm_est(keep= val rate rate_ll rate_ul);
    set out_parm(where=(parameter='intercept'));
    format rate rate_ll rate_ul 8.2;
    val= "mean number per year from negative binomial model without
covariate";
    rate=exp(estimate);
    rate_ll=exp(lowerwaldcl);
    rate_ul=exp(upperwaldcl);
  run;
```

where GOLD = COPD grade (2, 3 or 4), age = age at enrolment (40-49, 50-59, 60-69, ≥ 70 years), smoking = smoking status at enrolment (current and former smokers), exacHist = number of exacerbations reported in the 12 months prior to enrolment (one, two and equal or above three), country = countries in the study (Hong Kong, Philippines, Korea, Taiwan), n_exac = number of exacerbations during the study and logfuinyears = logarithm of the follow-up period in years.

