6.3.5. Severity and duration of AECOPD

Total number of exacerbations recorded during the study, exacerbation rate (number of exacerbation per patient-year) and the proportion of COPD patients experiencing a certain number of exacerbations will be presented overall and per bacterial/viral species. The exacerbation rate per year will be reported with and without correction for early withdrawal (see Section 11.3).

Total number of exacerbations recorded during the study, the mean exacerbation rate per year and the proportion of COPD patients experiencing a certain number of exacerbations will be presented overall and divided by AECOPD severity.

The number and proportion of COPD patients experiencing a certain number of exacerbations will be presented overall and by GOLD grade at enrolment.

CONFIDENTIAL

201112 (EPI-NTHI-001 BOD APA)
 Statistical Analysis Plan Amendment 2 Final

The number of patients that report at least 1 AECOPD will be tabulated and descriptive statistics (N, mean, median, SD, minimum, maximum, first and third quartiles) on the average length of AECOPD episodes, as estimated by the investigator, will be presented, for any, mild, moderate and severe AECOPD.

Number of days between 2 consecutive exacerbations, as estimated by the investigator, will be summarized using the same descriptive statistics.

Descriptive statistics of the number of patients according to their percentage of days within an exacerbation period out of the total observation period as estimated by the investigator will be presented. For this analysis, the exacerbations for which the end date was unknown were not excluded and the length was estimated by the investigator as the average length per severity grade.

Results from the chest X-rays during exacerbation visit will be tabulated.

The percentage of scheduled visit in which the status of the patient is stable/recovered, or not recovered will be tabulated.

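### SAP 11.3's ×13 annualisation of withdrawn patients can bias the withdrawal-corrected AECOPD rate in SAP 6.3.5 upward when patients leave after an exacerbation

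*SAP*

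**What the plan says.** SAP 11.3 replaces no missing measurements, with one exception: "The number of exacerbations per year will be extrapolated for patients withdrawing from the study". The value is obtained by "multiplying the number of exacerbations experienced by the patient by 13 and dividing by the number of 4-week periods the patient was followed up". The stated reason for working in 4-week blocks is "to avoid obtaining high imputed rates if a patient withdrew very early from the study after experiencing an exacerbation".

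SAP 6.3.5 uses this value: "The exacerbation rate per year will be reported with and without correction for early withdrawal", overall and by bacterial or viral species. The next paragraph, on severity, refers to "the mean exacerbation rate per year and the proportion of COPD patients experiencing a certain number of exacerbations".

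The secondary incidence endpoint is handled separately. SAP 6.3.4.4 fits a negative binomial model with "the logarithm of follow up time as an offset variable". SAP 6.3.4 defines the observation period as Visit 1 to Visit 3, or "from visit1 to the last visit performed for patients lost to follow up". For time to first exacerbation, SAP 6.3.5.2.1 instead censors at the date of last contact. SAP section 7 classes all analyses as descriptive.

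**The concern.** A rate estimated from 3 weeks of follow-up carries far less information than one estimated from 12 months. The 11.3 rule scales both to a year, and a plain average then gives them equal weight. That alone adds noise.

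It becomes bias when leaving is linked to the event. A patient who has an AECOPD and then withdraws has a short follow-up because an event occurred, so count divided by time is high by construction. This is also the situation that 11.3 says the blocks are meant to protect against.

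At stake is the figure that 6.3.5 labels as corrected for early withdrawal, and its per-pathogen versions, where events are fewer and one extrapolated patient weighs more. A reader could find it in visible conflict with the 6.3.4 rate in the same report.

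**Working it through.** **Inputs from the documents.** Enrolment: "The target is to enrol approximately 200 eligible moderate to very severe COPD patients" (Protocol 4.1). Protocol 9.2 assumes about 80% complete, so about 20% (40 of 200) withdraw. Protocol Table 13 considers rates of 0.2, 1, 2 and 3 per subject-year and overdispersion Φ of 1, 1.5 and 2.

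**Assumptions not in the documents.** The timing and cause of withdrawal; part-blocks rounded up unless stated; patient values averaged without weights.

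**Step 1: reproduce the plan's precision.** The documents give no figure for the correction itself. Table 13 gives the planned interval for a rate of 1.00 with T = n = 160 (200 × 0.80). The formula is n/T ± 1.96 × √(Φn)/T.
- Φ = 1: 1 ± 1.96 × √160/160 = 1 ± 0.155, or 0.85 to 1.15.
- Φ = 1.5: 1 ± 0.190, or 0.81 to 1.19.
- Φ = 2: 1 ± 0.219, or 0.78 to 1.22.

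All three agree with the table.

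**Step 2: the rule for one patient.** One AECOPD gives 1 × 13/blocks: 13 per year for 1 block, 6.5 for 2, 4.3 for 3, 1.0 for 13. Daily annualisation at day 14 would give 364/14 = 26, so the blocks halve that extreme. At day 40 the answer is 6.5 if part-blocks are rounded up and 13 if rounded down. Under 28 days, rounding down divides by zero.

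**Step 3: influence on a mean over 200 patients.** Let k patients leave in block 1 after one AECOPD, and the others average the true rate r. The total is (200 - k)r + 13k.
- r = 1, k = 5: 195 + 65 = 260; mean 1.30; the five supply 65/260 = 25%.
- r = 2, k = 5: 390 + 65 = 455; mean 2.28; 14%.
- r = 3, k = 5: 585 + 65 = 650; mean 3.25; 10%.
- r = 0.2, k = 3 (a plausible level for a single pathogen): 39.4 + 39 = 78.4; mean 0.39; 50%.

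**Step 4: simulation.** 200 patients, gamma-Poisson counts, true rate 1 per year, 20% withdrawing, follow-up measured to the actual date of leaving.

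| Withdrawal pattern | 11.3 corrected mean | Pooled events/person-time | Negative binomial with offset |
|---|---|---|---|
| Unrelated to AECOPD | 0.97 to 0.98 (1.02 rounded down) | about 1.00 | – |
| Half follow a first AECOPD | 1.17 | 0.96 | – |
| All follow a first AECOPD | 1.36 | 0.92 | – |
| All leave 14 days after an AECOPD (Φ = 1 / 1.5 / 2) | 1.34 / 1.36 / 1.33 | 1.00 / 0.95 / 0.91 | 1.00 / 1.00 / 1.01 |

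Under the last pattern the bias is +15% to +16% at rate 2 and +10% at rate 3 (Φ = 2). With only 10% withdrawing it is +18% at rate 1 (Φ = 1.5).

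Leavers within three blocks supply about 3% of the corrected total when withdrawal is unrelated to AECOPD, and about 22% to 35% at rate 1 when it follows one.

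**Step 5: where follow-up ends.** SAP 11.3 does not define it. If the last-visit definition of 6.3.4 is carried over, follow-up can stop at an AECOPD visit even when leaving is unrelated to it. The corrected mean is then 4% to 8% high at rates 1 to 3, and pooled person-time 4% to 5% high. About 10 to 16 patients per 200 have no visit after Visit 1: zero follow-up, hence zero blocks in 11.3 and log(0) as the offset in 6.3.4.4. Dropping them takes the corrected mean to 10% to 17% high.

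**Step 6: completers.** Their counts are not annualised, although Protocol Table 6 allows 175 + 175 = 350 to 203 + 203 = 406 days from Visit 1 to Visit 3.

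**The case against.** The strongest reply is that the plan already deals with unequal follow-up where it matters. The incidence endpoint, overall and by GOLD grade, severity, country and pathogen, comes from the offset model. The 11.3 figure is one descriptive summary, printed beside the uncorrected one. That stands, and it limits the point to 6.3.5.

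Second, the blocks do part of their job: 13 rather than 26 per year at day 14. That also stands. The cause of the bias is the equal weighting of annualised patient values, and blocks reduce it without removing it.

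Third, unweighted averaging is inferred. The mean rate is named in the by-severity paragraph, not in the sentence about correction, and 6.3.5 also describes the rate as exacerbations per patient-year. This is a fair caveat. But 11.3 yields a per-patient yearly number and no weights are given, so averaging is the natural reading. If the uncorrected figure is instead a plain mean count, it is no refuge: with 20% leaving at uniform times, mean follow-up is 0.8 + 0.2 × 0.5 = 0.90 year, so it is about 10% low.

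Fourth, rounding down contradicts the stated purpose of the blocks. Agreed; the main results above round up.

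A reader might infer that a few early leavers generally dominate the corrected rate, or that the AECOPD incidence endpoint is biased by this rule. The documents support neither. The early leavers' share is about 3% if withdrawal is unrelated to AECOPD and stays a minority at rate 1 even when it follows one; three patients reach half only at rates near 0.2 per year. SAP 6.3.4.4 does not use the ×13 rule.

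**Conclusion.** The point holds in a limited form and should be corrected. If patient values are averaged, the 11.3 correction overstates the yearly AECOPD rate when withdrawal follows an exacerbation: by about 17% to 36% at a true rate of 1 per year with 20% withdrawing, as the linked share goes from half to all. At those sizes the estimate (1.17 to 1.36) lies above the planned 0.85 to 1.15 for Φ = 1. The relative bias shrinks at higher rates and with fewer or less event-driven withdrawals. It is about -3% to +2% when withdrawal is unrelated to AECOPD and follow-up runs to the actual date of leaving.

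The size depends on a withdrawal pattern that the documents do not give. The lack of rules for part-blocks, zero blocks and the end of follow-up does not depend on any such assumption.

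**What to change.** In SAP 6.3.5, report the negative binomial offset rate of 6.3.4.4 as the yearly rate that allows for early withdrawal, overall, by severity and per pathogen. If a simple summary is preferred, use total AECOPD divided by total observed person-years, with completers' actual days included. The model is the better choice if frequent exacerbators leave selectively, because pooled person-time then runs somewhat low (0.91 to 1.00 in the simulation, against 1.00 to 1.01).

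For both, end each patient's observation at last contact rather than the last visit performed. This matches the censoring rule in 6.3.5.2.1 and requires the same change in 6.3.4.

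Delete the ×13 formula from 11.3 together with its status as the exception to non-replacement. Alternatively, keep it as a labelled sensitivity figure with part-blocks rounded up and a minimum of one block.

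The cost is SAP text and a simpler program, with no new data. The drawback is lower comparability with studies that used the 4-week extrapolation; keeping it as a sensitivity figure preserves that comparison.
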